6.3.5.2. Time to exacerbation

To investigate the effect of several baseline risk factors upon the time to first exacerbation since enrolment/first visit, Cox regression models will be fitted including several risk factors such as smoking status at enrolment (active smoker vs. former-smoker), number of exacerbation reported in the 12 months prior to enrolment (one, two and equal or above three), COPD grade at enrolment, age (40-49, 50-59, 60-69, ≥ 70 years), sex. Time to the first recurrence overall and by covariates will be depicted in Kaplan-Meier survival curves. Log-log survival curves will be displayed as well. If the proportionality of hazards assumption is met the log-log survival curves will be parallel for covariate strata. If there is an intersection between curves the covariate will be added as a stratification factor in the cox regression model.

To take into account that exacerbations may occur more than once over the follow-up time for a given patient, a Cox regression model for recurrent events using the counting process approach (Andersen, 1993) will be adopted (more details in section 6.3.5.2.1). The model will be fitted including smoking status at enrolment, history of exacerbation in the 12 months prior to enrolment, COPD severity at enrolment, age and sex as covariates.

Additional stratification/risk factor may be defined during the analyses.

CONFIDENTIAL

201112 (EPI-NTHI-001 BOD APA)
 Statistical Analysis Plan Amendment 2 Final

6.3.5.2.1. Statistical methods: survival analysisKaplan-Meier curves

Kaplan-Meier survival curves will be produced to represent the cumulative survival probability over time.

The code follows.

```
Proc lifetest data = <dataset> method = KM plot = (S, LLS);  

  time survt*Status(0);  

  strata smoking;  

run;
```

where survt = survival time in days (days to first exacerbation, for censored data the date of last contact will be used), status = censoring variable (0 = censored, 1 = event), and smoking = smoking status at enrolment (current and former smokers). The PLOTS=(S,LLS) option produces log-log curves as well as survival curves.

Cox Proportional Hazards regression model

To investigate the effect of several baseline risk factors upon the time to first exacerbation, Cox Proportional Hazards (PH) regression models will be fitted.

SAS codes

```
Proc phreg data = <dataset>;  

  class GOLD age exacHist sex  

  model survt*Status(0) = gold age exacHist / ties = exact rl;  

  strata smoking;  

run;
```

where GOLD = GOLD grade (2,3 or 4), age = age at enrolment (40-49, 50-59, 60-69, ≥ 70 years), smoking = smoking status at enrolment (current and former smokers), exacHist = number of exacerbations reported in the 12 months prior to enrolment (one, two and equal or above three) and sex (male and female). For the scope of the example, the variable *smoking* is considered to be a stratification factor.

Recurrent event survival analysisSAS code

```
Proc phreg data = <dataset> covs(aggregate);  

  model (start,stop)*event(0) = exacerbationHistory smoker;  

  id pid;  

run;
```

The code (START,STOP)*EVENT(0) in the MODEL statement indicates that the time intervals for each observation are defined by the variables START and STOP and that EVENT = 0 denotes a censored observation.

CONFIDENTIAL201112 (EPI-NTHI-001 BOD APA)
Statistical Analysis Plan Amendment 2 Final**6.3.6. Impact of AECOPD on HRQOL**

Descriptive statistics (N, mean, median, SD, minimum, maximum, first and third quartiles) on the CAT and SGRQ-C scores (total score and symptoms, activity and impacts component scores) will be tabulated at each stable scheduled visit, overall and by COPD GOLD grade at enrolment.

CAT and SGRQ-C (total score and symptoms, activity and impacts component scores) changes from first visit to final scheduled visit will be displayed according to the number of exacerbation occurred in the observation period. Correlation will be evaluated using Spearman's rank-order correlation coefficient.

Descriptive statistics (N, mean, median, SD, minimum, maximum, first and third quartiles) on the CAT score will be tabulated for any stable and any mild, moderate or severe exacerbation visit.

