6.3.4.4. Statistical methods: analysis of count data with overdispersion

The incidence rate and its 95% CI will be estimated using the Generalised Linear Model (GLM) assuming a negative binomial distribution for the response variable with logarithm as link function and the logarithm of follow up time as an offset variable. The fit of the model will be examined using Q-Q plots of standardised residuals. It is possible that the negative binomial model will not converge due to underdispersion of data; in such cases, to overcome the problem of underdispersion, a Poisson model will be used to obtain the incidence rate and its 95% CI.

SAS codes:

```
proc genmod data = <dataset>;
  class gold age smoking exacHist;
  model n_exac = GOLD age smoking exacHist country
    / link=log dist=negbin offset=logfuinyears ;
  ods output parameterestimates=out_parm nobs=nobs;
  ods exclude modelinfo modelfit parameterestimates nobs;
  run;

  data parm_est(keep= val rate rate_ll rate_ul);
    set out_parm(where=(parameter='intercept'));
    format rate rate_ll rate_ul 8.2;
    val= "mean number per year from negative binomial model without
covariate";
    rate=exp(estimate);
    rate_ll=exp(lowerwaldcl);
    rate_ul=exp(upperwaldcl);
  run;
```

where GOLD = COPD grade (2, 3 or 4), age = age at enrolment (40-49, 50-59, 60-69, ≥ 70 years), smoking = smoking status at enrolment (current and former smokers), exacHist = number of exacerbations reported in the 12 months prior to enrolment (one, two and equal or above three), country = countries in the study (Hong Kong, Philippines, Korea, Taiwan), n_exac = number of exacerbations during the study and logfuinyears = logarithm of the follow-up period in years.

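### The printed program for the recurrent-exacerbation Cox model omits three of the five covariates named in the SAP text and has no CLASS statement, so it does not fit the stated model

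*SAP*

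**What the plan says.** SAP 6.3.5.2 describes two Cox analyses.

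**Recurrent events.** The rule for the counting-process model begins "The model will be fitted including smoking status at enrolment, history of exacerbation in the 12 months prior to enrolment, COPD severity at enrolment, age". The end of the same sentence, "COPD severity at enrolment, age and sex as covariates", brings in sex as the fifth covariate. The section sends the reader to 6.3.5.2.1 for more detail. The recurrent-event program there opens with "Proc phreg data = <dataset> covs(aggregate" and a closing bracket. Its model line is "model (start,stop)*event(0) = exacerbationHistory smoker", followed by an ID statement on the patient identifier. It has no CLASS or STRATA statement. The note beneath it explains only the start/stop syntax.

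**First event.** Section 6.3.5.2 lists smoking, history, COPD grade, age and sex as risk factors, with history coded as "number of exacerbation reported in the 12 months prior to enrolment (one, two and equal or above three". The program has "class GOLD age exacHist sex", with no closing semicolon, and then "model survt*Status(0) = gold age exacHist / ties = exact rl", with smoking as a stratification factor. Sex is in CLASS but not in MODEL.

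**Counts.** The negative binomial program in SAP 6.3.4.4 has "class gold age smoking exacHist" and includes country in MODEL. Country is not in CLASS. The section defines it by four names: Hong Kong, Philippines, Korea and Taiwan.

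The SAP does not say whether text or code prevails when they differ.

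**The concern.** A programmer who takes 6.3.5.2.1 as the specification will fit a different model from the one the text commits to. The history and smoking hazard ratios would then not be adjusted for COPD severity, age and sex, although a reader of 6.3.5.2 would assume that they were. The analysis would also give no severity, age or sex effect for recurrent AECOPD, which the text implies it will estimate.

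The COVS(AGGREGATE) option with the ID statement does not repair this. It corrects standard errors for repeated events within a patient and leaves the set of covariates unchanged.

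**Working it through.** The documents give no sample size, power or event figure for this model, so there is no planned figure to reproduce. The check sets text against code.

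**1. Covariates.**

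| Covariate in SAP 6.3.5.2 | Levels in the first-event coding | Parameters | In the printed recurrent-event program |
|---|---|---|---|
| Smoking status | 2 (current, former) | 1 | yes, as `smoker` |
| Exacerbation history | 3 (one, two, three or more) | 2 | yes, as `exacerbationHistory`, one term |
| COPD severity (GOLD) | 3 (grades 2, 3, 4) | 2 | no |
| Age | 4 bands | 3 | no |
| Sex | 2 | 1 | no |

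Stated model: 1 + 2 + 2 + 3 + 1 = 9 parameters from five covariates. Printed model: 2 parameters from two covariates, if both are numeric. The codings are those given for the first-event model; the SAP does not restate them for the recurrent-event model.

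**2. Variable names.** The other programs use `exacHist` and `smoking`, and the SAP defines both. `exacerbationHistory` and `smoker` appear only in the recurrent-event program and are not defined, so their coding cannot be looked up.

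**3. Effect of the missing CLASS statement.** A numeric variable outside CLASS gets one coefficient, b. If history is scored 1, 2, 3, the hazard ratio for two versus one is exp(b), and for three or more versus one it is exp(2b), the square of the first. A categorical model leaves the two ratios free. Other codings behave differently:
- A two-level numeric variable (one versus two or more) carries no such constraint.
- A character variable would not run without CLASS.
- Smoking, with two levels, is unaffected if it is numeric.

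A simple yes/no for any prior event is ruled out, because protocol 4.2 requires at least one moderate or severe AECOPD in the year before entry.

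**4. Effect of the omitted covariates.** The history ratio shifts only if an omitted covariate is related both to history and to the exacerbation rate. The risk groups in SAP 11.2.1 pair GOLD 3 or 4 with two or more exacerbations per year, so a link between history and GOLD is plausible. The documents do not give the strength of that link or the effect of GOLD on the rate within this cohort. No size can be calculated.

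**5. Companion programs.** In the first-event block, the missing semicolon would make SAS read the MODEL line as part of CLASS, so the block cannot run as printed. Even with that repaired, sex would not be fitted. In the count block, country outside CLASS is not fitted as a four-level factor under any coding.

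**The case against.** The strongest reply is that the text already names the right model, and an analyst who follows it will fit all five covariates. The code looks like a syntax template: it uses a placeholder dataset name and ad hoc variable names, and its only commentary concerns start/stop notation. The text also lets a covariate move into strata when log-log curves cross and allows further factors to be defined, so no printed MODEL line can be final. The mock tables are in a separate document, so what would actually be reported is unknown. Protocol 9.6 contains no Cox model, and SAP section 7 limits all analyses to supportive or hypothesis-generating use.

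Much of this stands. The harm arises only if the code is run as printed, and it does not reach the primary analysis. Three parts do not remove the contradiction:
- The only example label in 6.3.5.2.1 is attached to stratifying by smoking in the first-event block. The recurrent-event block carries none.
- Moving a covariate to strata still accounts for it, and permission to add factors is not permission to drop named ones. The recurrent-event program has no STRATA statement.
- The text cites 6.3.5.2.1 as its detail, with no rule on which prevails.

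**Conclusion.** The recurrent-event program contradicts the model it is meant to implement: two covariates instead of five, undefined variable names and no CLASS statement. Run as printed, the history and smoking hazard ratios are unadjusted for COPD severity, age and sex, and history enters linearly if it is a numeric code for one, two, or three or more events.

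A reader might infer more than the documents support:
- **That the history effect is confounded.** The code shows only that it is unadjusted. Bias needs associations that the documents do not quantify.
- **That history is necessarily forced to be linear.** This depends on the coding of an undefined variable.
- **That country would silently be fitted as a slope in the count model.** That needs a numeric code. The SAP lists country names, and a character variable outside CLASS would stop with an error. That block also extracts only the intercept, under a label saying the model has no covariate.

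The first-event and count programs need minor alignment only. The point concerns a descriptive analysis under the secondary objectives, and the size of any effect on its estimates is unknown.

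**What to change.** In SAP 6.3.5.2.1, change the recurrent-event program to:

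`CLASS GOLD age exacHist smoking sex;`
`MODEL (start,stop)*event(0) = smoking exacHist GOLD age sex;`

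Keep COVS(AGGREGATE) and `ID pid`. Use the variable names and codings already defined for the first-event model. Move a covariate from MODEL to STRATA only where the proportional-hazards check in 6.3.5.2 calls for it. Add one sentence saying that the text governs where text and code differ.

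Minor alignments: in the first-event program, close the CLASS statement with a semicolon and add sex to MODEL; in the count program of 6.3.4.4, add country to CLASS if it stays in MODEL.

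The cost is a few program lines and one sentence. No data collection, sample size or primary analysis changes.

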 - For each AECOPD: AECOPD visit (within 96 hours of the onset of the symptoms) and follow-up phone call(s) (at least every 2 weeks until the AECOPD has resolved). Follow-up phone contacts will define end of AECOPD.
- **COPD symptoms**
Subjects will be asked to record their COPD symptoms in an electronic Diary Card on a daily basis:
 - Daily in the morning throughout the study: Morning symptoms questionnaire.
 - Daily at bedtime throughout the study: EXACT-PRO (EXAcerbations of Chronic Pulmonary Disease Tool - Patient Reported Outcome) questionnaire.
- **Biological samples:**
 - **Sputum samples** collected at site (spontaneous or induced, as per investigator judgement) will be collected at each study visit at the site (scheduled [stable] visits and AECOPD visits) if, in the opinion of the investigator, it is safe for the subject.

Or

- **Sputum sample collected at subject's home (spontaneous).** Self-collection of the sputum sample will be allowed in specific cases, where the first dose of antibiotics absolutely needs to be taken before an AECOPD visit can take place. This is not allowed at scheduled visits when subject should be in stable condition.

Note: The sputum samples collected during AECOPD should preferably be obtained before administration of the first dose of antibiotics to treat the AECOPD (if applicable).

- **Blood samples** for biomarker testing will be collected at Visit 1 (M0) and Visit 3 (M12).

- **HRQOL assessments**

- Subjects will be asked to complete the COPD assessment Test (*CAT*) at each study visit (scheduled [stable] visits and AECOPD visits).
- Subjects will be asked to complete the St. George's Respiratory Questionnaire for COPD patients (SGRQ-C) at each scheduled (stable) study visit (Visit 1 [Month 0], Visit 2 [Month 6] and at Visit 3 [Month 12]).
- Pre- and post-bronchodilator spirometry assessments will be done for all subjects at Screening Visit (pre-Month 0) and at Visit 3 (Month 12).

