3.2. Secondary objectives

- To evaluate the concordance between PCR and bacteriological methods data in sputum for potential bacterial pathogens.
- To estimate the proportion of potential bacterial and viral pathogens (overall and by species) detected in sputum of stable COPD patients, by GOLD grade.
- To estimate the proportion of potential bacterial and viral pathogens (overall and by species) detected in sputum during AECOPD, by severity of AECOPD.
- To estimate the incidence rate of all-cause AECOPD, overall and by GOLD grade.
- To describe the severity and duration of all-cause AECOPD, overall and by GOLD grade.
- To assess the impact of all-cause AECOPD on HRQOL.
- To assess the impact of all-cause AECOPD on lung function.
- To assess the impact of all-cause AECOPD on healthcare utilisation.

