4.2. Secondary endpoints

- Occurrence of potential bacterial pathogens in sputum of stable COPD patients and during AECOPD, as measured by real-time qualitative PCR/ quantitative PCR and compared to data from bacteriological methods, over the course of 1 year:
 - Including (but not necessarily limited to) *H. influenzae*, *M. catarrhalis*, *S. pneumoniae*, *S. aureus* and *P. aeruginosa*.
- Occurrence of potential bacterial and viral pathogens (overall and by species) in sputum of stable COPD patients by GOLD grade, over the course of 1 year.
- Occurrence of potential bacterial and viral pathogens (overall and by species) in sputum during AECOPD by severity of AECOPD, over the course of 1 year.
- Incidence rate (per patient per year) of AECOPD, overall and by GOLD grade, over the course of 1 year.
- Severity of AECOPD, overall and by GOLD grade, over the course of 1 year.
- Duration of AECOPD, overall and by AECOPD severity, over the course of 1 year.
- CAT score in stable COPD patients and during AECOPD, over the course of 1 year.
- SGRQ-C score in stable COPD patients, over the course of 1 year.
- FEV₁% of predicted normal value in stable COPD patients, at Pre-Month 0 and Month 12.
- Healthcare utilisation, over the course of 1 year.

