6.3.8. Impact of AECOPD on healthcare utilisation

Descriptive statistics of the daily number of healthcare utilisation (number of HCU in the relevant period divided by the number of days) within the stable period and within the exacerbation period will be presented overall and divided by the following unscheduled visits:

1. Number of physician office consultations,
2. Number of visits to urgent care,
3. Number of visits to emergency department,
4. Number of hospitalizations.

Healthcare use for each patient will be obtained through review of the patient's medical record (aided by patient daily self-reporting in the eDiary).

Healthcare utilisation will be summarized according to country and COPD grade at enrolment. In addition, healthcare utilisation will be summarized by AECOPD severity during exacerbations.

Overall HCU [total number and divided by type of HCU] per patient will be correlated to the number of exacerbations experienced during the observation time.

Current medication for COPD and additional COPD treatments prescribed by primary and secondary care physicians within the stable period and within the exacerbation period will be described by drug category (chronic use for COPD and chronic use for other

CONFIDENTIAL

201112 (EPI-NTHI-001 BOD APA)
 Statistical Analysis Plan Amendment 2 Final

disorders) overall, by country and by COPD grade at enrolment. In addition, percentage of patients with or without inhaled corticosteroids at enrolment and incidence rate of confirmed exacerbation by use of corticosteroids will be tabulated.

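### SAP 6.3.6 gives the acute effect of AECOPD on CAT no within-patient contrast, although each patient's stable and AECOPD scores are both collected

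*SAP*

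**What the plan says.** The objective in SAP 3.2 is "To assess the impact of all-cause AECOPD on HRQOL". The matching endpoint in SAP 4.2 is "CAT score in stable COPD patients and during AECOPD, over the course of 1 year". Protocol section 3 has patients complete CAT "at each study visit (scheduled [stable] visits and AECOPD visits"). Protocol Tables 4 and 5 place it at Visits 1, 2 and 3 and at every AECOPD visit, and Protocol 6.4.3.10 makes it the only HRQOL questionnaire at an AECOPD visit.

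SAP 6.3.6 (Amendment 2) plans three analyses:

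- CAT and SGRQ-C statistics that "will be tabulated at each stable scheduled visit, overall and by COPD GOLD grade at enrolment".
- CAT and SGRQ-C for which "changes from first visit to final scheduled visit will be displayed according to the number of exacerbation occurred in the observation period", with the added sentence "Correlation will be evaluated using Spearman's rank-order correlation coefficient".
- Descriptive statistics that "on the CAT score will be tabulated for any stable and any mild, moderate or severe exacerbation visit".

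Only the third uses a CAT score taken during an exacerbation. The section names no difference, pairing, confidence interval or model for it, and does not say whether its unit is the visit or the patient. SAP section 7 calls all analyses descriptive, for supportive use or hypothesis generation.

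**The concern.** The cohort can serve as its own control. Patients enter in a stable state, give a CAT score at Visit 1, and give another at each AECOPD visit. The planned table sets the two states side by side without linking them, and different sets of patients stand behind its rows. Those who never exacerbate are on the stable side only. If rows are visits, those who exacerbate often are on the AECOPD side several times. The mild, moderate and severe rows can likewise come from partly different patients, although one patient may contribute to more than one.

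If frequent exacerbators have a different stable CAT from the rest, the gap between rows is the acute change plus a between-patient difference. Protocol 1.1 gives a reason to expect this, since it links higher exacerbation rates to poorer quality of life. It gives no size.

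The section is titled as the impact of AECOPD on HRQOL, so readers will be inclined to subtract the rows. The SAP uses within-patient methods elsewhere: GEE for pathogen proportions (6.2.1) and patient-stratified conditional logistic regression for pathogens (6.4.4).

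**Working it through.** **Figures in the plan.** No SD, effect size or precision is stated for CAT, so there is no CAT figure to reproduce. The event-rate inputs come from Protocol 9.2, Table 13, whose interval is n/T ± 1.96·sqrt(Φn/T²). At T = 160 and 1 AECOPD per year this gives 0.85–1.15, 0.81–1.19 and 0.78–1.22 for Φ = 1, 1.5 and 2, as printed.

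**Inputs from the documents.** Mean m = 1 AECOPD visit per subject (Protocol 9.2); Φ = 1, 1.5 and 2 (Table 13).

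**Assumptions not in the documents.** Between-patient SD of stable CAT = 7; correlation r = 0.1 to 0.4 between stable CAT and log event rate; the CAT table is by visit; patients contribute equally to the stable side; every AECOPD has a visit with a CAT.

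**Step 1: who supplies the AECOPD visits.** Take event counts as Poisson at Φ = 1 and negative binomial otherwise, with k = (Φ − 1)/m. The share of visits from patients with two or more events is 1 − P(1)/m. For Φ = 2, P(1) = 0.25, so the share is 1 − 0.25 = 75%.

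| Φ | Patients with no AECOPD | Patients with ≥2 | AECOPD visits from patients with ≥2 |
|---|---|---|---|
| 1 | 37% | 26% | 63% |
| 1.5 | 44% | 26% | 70% |
| 2 | 50% | 25% | 75% |

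At 0.2 per year the last column would be 18%, 43% and 56%, so the concentration depends on the event rate.

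**Step 2: case-mix part of the row difference.** With lognormal event rates, the log rate has SD sqrt(ln(1 + k)), which is sqrt(ln Φ) at m = 1. Weighting patients by event rate shifts mean stable CAT by

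excess = SD · r · sqrt(ln Φ).

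- Φ = 1: sqrt(ln 1) = 0, so the excess is 0 for any r.
- Φ = 1.5: sqrt(ln 1.5) = 0.637. 7 × 0.1 × 0.637 = 0.4 and 7 × 0.4 × 0.637 = 1.8 points.
- Φ = 2: sqrt(ln 2) = 0.833. 7 × 0.1 × 0.833 = 0.6 and 7 × 0.4 × 0.833 = 2.3 points.
- r = 0: the excess is 0 for any Φ.

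A simulation of the Φ = 2 case with an assumed acute rise of 5 points gave row differences of 5.61, 6.16, 6.75 and 7.31 for r = 0.1, 0.2, 0.3 and 0.4. The excess is thus 0.61 to 2.31, in line with the formula.

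**Step 3: another shape for the rates.** With gamma rates the excess is ρ · sqrt(k) · SD, where ρ is the correlation of stable CAT with the rate itself. For ρ = 0.1 to 0.5 this is 0.5 to 2.5 points at Φ = 1.5 and 0.7 to 3.5 at Φ = 2. With SD 5 to 9 and ρ = 0.3 it is 1.1 to 1.9 and 1.5 to 2.7.

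**Step 4: the paired difference.** In the gamma simulation (200,000 patients per scenario, true rise 5), AECOPD score minus the same patient's stable score was 4.98 to 5.02 in every scenario. The unpaired difference ran up to 8.53 (Φ = 2, ρ = 0.5).

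**The case against.** The strongest reply is that the plan makes no such subtraction. SAP 6.3.6 defines no stable-minus-AECOPD difference, section 7 keeps everything descriptive, and the table matches the endpoint. That stands. A reader might infer that the plan itself mistakes case mix for effect; the documents show only that the table invites the misreading.

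A reader might also take this table as the only direct evidence on impact. It is not. The first-to-final change in CAT and SGRQ-C is within patient, and the objective is not limited to acute effects. The firm conclusions that Protocol 3.1 expects concern decline, which that analysis addresses. SAP 6.4.1 and 12.2 also describe EXACT scores around each event, with a baseline from days 14 to 8 before onset. EXACT is tertiary and is not presented as an HRQOL measure, so it qualifies the point without replacing a CAT contrast. The first-to-final change contains no AECOPD-visit score.

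The row structure is partly inferred, because the unit is not stated and the mock tables are in a separate document. If each patient counted once, the repeat weighting would go, but patients without an AECOPD would still be on the stable side only.

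The direction is open too. Exacerbations known only from medical records (Protocol 3.1.1, SAP 12.4) give no AECOPD-visit CAT. If these are often the hospitalised cases, sicker patients could be under-represented. Protocol 4.2 requires at least one moderate or severe AECOPD in the prior year, which narrows the contrast between patients.

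Finally, a reader might extend the point to SAP 6.3.8, where healthcare use "within the stable period and within the exacerbation period will be presented overall". That analysis divides counts by days and states no event weighting, and the calculations above cover CAT only. They do not support the same conclusion there.

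**Conclusion.** The point holds as a gap in method: the acute change in CAT has no within-patient estimate, although the data for one are collected. Under the assumptions listed, the case-mix part of the row difference is 0 at Φ = 1, about 0.4 to 1.8 CAT points at Φ = 1.5 and 0.6 to 2.3 at Φ = 2.

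This range illustrates the possible size; it does not estimate a bias in this study. The SD and the correlation are assumed, and Φ = 2 is the highest of the three values in Table 13. A reader might turn the range into a percentage overstatement, but that would also need a true acute rise, which the documents do not give. Nor do they establish that the row difference will be inflated: the excess vanishes if event rate and stable CAT are unrelated, and missed AECOPD visits could change the direction. Pairing removes stable differences between patients in either direction, but not selection from missed visits. This is a cheap improvement to a secondary analysis.

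**What to change.** In SAP 6.3.6, for each AECOPD visit with a CAT score, add the change from the same patient's last preceding confirmed stable visit. Summarise it overall and by AECOPD severity, with a 95% CI from a GEE or mixed model clustered on patient. Keep the existing table as description, and report the number of patients as well as visits in each row.

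The cost is SAP wording and one extra table, with no new data collection. There are two limits to state. AECOPD visits with no CAT, or with no earlier stable CAT, drop out; CAT is not collected at screening, so an AECOPD before Visit 1 has no reference. The stable reference may also be about six months old, because Protocol Table 6 allows 175 to 203 days between scheduled visits, so time and season can enter the change.
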